3.5. Study diagram

3.6. Trial Flowchart

	Screen visit	Record collection	Third visit	Follow up 6 months	Follow up 12 months	Follow up 18 months	Follow up End result
Informed consent		X					
Physical/Oral examination	X			X	X	X	X
Clinical photograph (if needed)		X		X	X	X	X
Panoramic radiograph (if needed)	X						X
Long cone apical radiograph (if needed)	X			X	X	X	
CBCT scan (if needed)					X		
Identification as potential inclusion in the study	X						
Inclusion in one of the groups and randomized treatment assignment		X					
Start of the assigned treatment (expansion, extraction deciduous canine/molar or no treatment)			X	X	X	X	
Surgical exposure of the maxillary permanent canine					X	X	

4. Selection and withdrawal of subjects

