4.3. Expected duration of trial

The trial will start at the first screening visit, where physical/oral examination will take place. If needed, standard radiographic screening images will be taken as well. If the patient is identified as complying with the inclusion criteria, a second visit will be programmed for the collection of standard orthodontic records and randomization for inclusion in any of the groups. The assigned interceptive treatment will start on a third visit. After a maximum of 6 months of interceptive treatment, follow up visits will be scheduled after 6, 12 and 18 months. At any of those recalls, if the canine has erupted, the patients may opt to start regular orthodontic treatment with fixed appliances if needed or desired (average duration of 24 months) and a last follow up visit will be programmed after the end of this treatment for evaluation of the final canine position.

5. Trial Procedures

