5.1. By visit

Screening visit

Patients come to our service seeking orthodontic advice. After physical/oral examination, a panoramic radiograph will be taken if considered necessary. Patients needing interceptive treatment and complying with the selection criteria will be identified.

Second Visit (Record taking)

Clinical photographs and orthodontic study casts, constituting normal orthodontic records for adequate diagnostics and treatment planning will be taken, as well as a standard long cone apical radiograph (LCAR) to determine the position of the canine. Depending on the obtained parameters related to canine position and angulation, the patient will be included in one of the groups detailed in chapters 3 and 4. The patient and parents will be informed about the need for treatment and they will be asked for consent when using the data for the purposes of the study. They will be given the informed consent, included in our regular contract for orthodontic treatment, with all the necessary details and information.

Third visit

If the patient decides to start treatment, the assigned treatment option will start (expansion, extraction of deciduous canine/molar or no treatment). Patients in the expansion group will be in treatment during a maximum of 6 months taking on average 4 and maximum 6 consultations. After

interceptive treatment with a removable expansion appliance, it might be necessary to wear the modified removable appliance at night for an extended period of 2 months.

Follow up 6 months

- If the canine has erupted, a reevaluation of the specific presenting malocclusion will be performed and the need for further orthopedic or fixed appliance treatment will be discussed with the patient or his/her parents/guardians. Normal orthodontic treatment can be performed if desired. Only at the end of orthodontic treatment or, in case of no treatment need, at the end of late mixed dentition transition into permanent dentition, a last follow up visit will be planned in order to evaluate the end result.
- If the canine has not erupted yet, a long cone apical radiograph will be taken for evaluation of the canine position and reevaluation will take place after 6 months (= follow up visit 12 months).

Follow up 12 months

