Randomisation will only be used when the different treatment options could be equally beneficial to the patient, with the objective of identifying possible differences in treatment outcomes. There is no new intervention to test, which minimizes the risk for negative impact.

10. Direct access to source data and documents

The investigators and the involved institutions will permit trial-related monitoring, audits, EC review, and regulatory inspections (where appropriate) by providing direct access to source data and other documents (i.e. patients' case sheets, X-ray reports, etc.).

11. Ethics and regulatory approvals

The trial will be conducted in compliance with the principles of the Declaration of Helsinki (2013), the principles of GCP and in accordance with all applicable regulatory requirements. This protocol and related documents will be submitted for review to the Ethics Committee of the UZ/KU Leuven for Clinical Trial Authorization.

The Study can and will be conducted only on the basis of prior informed consent by the Subjects, or their legal representatives, to participate in the Study. The Participating Site shall obtain a signed informed consent form (ICF) for all patients prior to their enrolment and participation in the Study in compliance with all applicable laws, regulations and the approval of the UZ/KU Leuven Ethics Committee. The Participating Site shall retain such ICFs in accordance with the requirements of all applicable regulatory agencies and laws.

The Investigator and the Participating Site shall treat all information and data relating to the Study disclosed to Participating Site and/or Investigator in this Study as confidential and shall not disclose

such information to any third parties or use such information for any purpose other than the performance of the Study. The collection, processing and disclosure of personal data, such as patient health and medical information is subject to compliance with applicable personal data protection and the processing of personal data (Directive 95/46/EC and Belgian law of December 8, 1992 on the Protection of the Privacy in relation to the Processing of Personal Data).

In this study, data will be coded.

*(Data are **anonymous** if no one, not even the researcher, can connect the data to the individual who provided it. No identifying information is collected from the individual.*

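### The random arm is assigned at the second visit but the decision to start it comes at the third, with no prior agreement to accept any arm and no assurance that decliners are followed

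*Combined protocol and SAP*

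**What the plan says.** **Timing of the draw.** Section 4.3 states that "a second visit will be programmed for the collection of standard orthodontic records and randomization for inclusion in any of the groups". The flowchart in 3.6 agrees: its row "Inclusion in one of the groups and randomized treatment assignment" is marked under record collection, which is the second visit. Informed consent is marked in the same column, and the flowchart does not order the two.

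**Start of the assigned option.** Section 4.3 gives it without a condition: "The assigned interceptive treatment will start on a third visit". Section 5.1 adds one: "If the patient decides to start treatment, the assigned treatment option will start". The options listed there include no treatment.

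**Consent.** In 5.1 the account of the second visit runs from records, to the statement that "the patient will be included in one of the groups detailed in chapters 3 and 4", to information about the need for treatment, and then to consent. Of the consent it says that "they will be asked for consent when using the data for the purposes of the study", followed by "They will be given the informed consent, included in our regular contract for orthodontic treatment, with all the necessary details and information". Section 11 requires each site to "obtain a signed informed consent form (ICF) for all patients prior to their enrolment and participation in the Study".

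**Eligibility.** Sections 4.1 and 4.2 list dental and medical criteria. Neither mentions willingness to be randomised or to accept whichever of the three arms is drawn.

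**Follow-up and analysis.** Section 7.3 ends treatment or follow-up when the patient does not comply or the family wishes to discontinue. Section 8.2 specifies an intent-to-treat analysis and gives no rule for missing 18-month outcomes.

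**The concern.** The three arms cannot be hidden from families. These families came for orthodontic advice and, under 5.1, are told about a need for treatment; one arm then offers none. If the decision to go ahead comes after the arm is drawn and known, refusal may differ between expansion, extraction and no treatment. It may also be related to how favourable the canine looks.

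Intent-to-treat protects the comparison only if the outcomes of those who decline are collected. The plan does not say that they will be, and 7.3 allows follow-up to stop. The analysed groups could then be those who accepted their arm rather than those who were randomised to it. This selection would arise at entry, before any treatment, and better ordering of the steps would largely avoid it.

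**Working it through.** **1. The sequence, read across sections**

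| Step | 4.3 | 3.6 flowchart | 5.1 | 11 |
|---|---|---|---|---|
| Random assignment | Second visit | Second visit | Not mentioned at the second visit; treated as already made at the third | – |
| Consent | – | Second visit, order not shown | Second visit, written after group inclusion | Before enrolment and participation |
| Start | Third visit, unconditional | Third visit | Third visit, if the patient decides to start | – |

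Two things follow. First, the option is already assigned when the third-visit decision is taken, so a decision point lies between the draw and the start. Second, the group inclusion in 5.1 depends on canine position and angulation, so it can mean the diagnostic stratum (for example nCLA or nCLB) rather than the random arm. Section 5.1 never says when the arm is drawn or disclosed.

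**2. The plan's own sample size**

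Inputs from 8.1: success 50% and 75%, two-sided alpha 0.05/3 = 0.0167, power 80%. With pooled variance and no continuity correction,

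n = [z(1−α/2)·√(2·p̄·(1−p̄)) + z(power)·√(p1(1−p1) + p2(1−p2))]² / (p2−p1)²

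= [2.394·√0.46875 + 0.842·√0.4375]² / 0.0625 ≈ 77.1, rounded up to 78.

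This matches the stated 78 per group (power 80.5%). At the planned 100 per group, power is 90.3%.

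**3. Loss of numbers, if equal in all arms (assumed rates)**

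- 10% loss, 90 per group: power 86.6%.
- 20% loss, 80 per group: power 81.7%.
- 22% loss, 78 per group: power 80.5%.

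The increase to 100, made for the prediction model, therefore absorbs equal losses of up to 22%.

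**4. Shift in one arm's rate when decliners are lost (assumed rates)**

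Take true success in the no-treatment arm as 50%, decliner share f and decliner success s. The rate among those remaining is (0.50 − f·s)/(1 − f).

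| f | s = 30% | s = 70% |
|---|---|---|
| 10% | (0.50 − 0.03)/0.90 = 52.2% | (0.50 − 0.07)/0.90 = 47.8% |
| 20% | (0.50 − 0.06)/0.80 = 55.0% | (0.50 − 0.14)/0.80 = 45.0% |

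The shift is 2.2 points at 10% and 5 points at 20%, in either direction.

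**5. Effect on the test (assumed rates)**

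Suppose there is no true difference (50% in both arms), one arm loses patients, and the leavers' success is 25% or 75%. At 10% loss the apparent difference is 2.8 points and the rejection rate about 2.5%. At 20% loss these become 6.3 points and about 6.0%. The nominal rate is 1.67%. A larger sample does not remove this.

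**6. If non-starters are all followed instead**

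Suppose a share of an active arm does not start and has the 50% success rate. The arm's true rate is then 0.75 − 0.25 × share. At 10% non-start it is 72.5% (power 81.5% at 100 per group), and at 20% it is 70% (power 69.3%). Full follow-up removes the selection but not the dilution, so willingness to accept any arm should also be settled before the draw.

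**The case against.** - **Randomisation before consent.** A reader might infer from the order of sentences in 5.1 that patients are allocated first and asked for consent afterwards. The documents do not support that. Section 11 requires a signed form before enrolment, the flowchart shows no order within the visit, and the group in 5.1 may be the stratum. What stands is that 5.1 and section 11 need to be reconciled.
- **Consent to data use only.** A reader might also infer that consent never covers random allocation. Section 11 speaks of consent to take part in the study, 5.1 promises full details, and the consent form is not among the text available here. Its content cannot be judged. What stands is that 5.1 names only data use.
- **Freedom to decline exists in every trial.** True, and the third-visit sentence also covers the non-randomised groups. But a decision point written into the schedule after assignment differs from ordinary withdrawal, and can be moved earlier.
- **Intent-to-treat and stratification already protect.** Intent-to-treat does so only for patients whose outcome is collected. Stratification by canine sector limits selection through that measure, but not through family preference or other prognostic features.
- **Numbers are sufficient.** This stands: a loss of 20 from 100 leaves 80, above the required 78. The issue is arm-dependent selection, not a shortfall in power.

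**Conclusion.** The concern holds as a gap in the plan. The arm is assigned at the second visit, the decision to start it comes at the third, no criterion secures prior willingness to accept any arm, and follow-up may stop for those who do not continue. Loss of outcomes that depends on the arm is therefore possible and unguarded.

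Its size and direction are unknown. The shift of about 2 to 5 points in one arm rests on assumed decline rates of 10% to 20% and an assumed 20-point difference in decliners' success. It illustrates what could happen and does not estimate what will. A reader should not take it as a demonstrated bias, nor as evidence that the trial is too small. The correction should be made because it is cheap and the selection is largely avoidable.

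**What to change.** 1. **4.1.** For nCLA and nCLB, add a criterion such as: *patient and parents have given signed consent to random allocation among expansion, extraction and no treatment and to follow-up to 18 months, and are willing to accept any of the three.*
2. **4.3, 5.1 and 3.6.** State one order: records and stratum; consent and the decision to take part; then the draw and its disclosure, as close to the start of the assigned option as logistics allow. Disclosure at the third visit itself may not be feasible without another visit, so it should not be made a fixed requirement.
3. **5.1.** Remove the post-allocation condition on starting for randomised patients, say whether group means stratum or arm, and align the order and scope of consent with section 11. The right to withdraw is unaffected.
4. **7.3 and 8.2.** Separate the stopping of treatment, which is not at issue here, from the collection of outcomes. State that every randomised patient who does not withdraw consent to data collection is followed to 18 months and analysed in the assigned arm whether or not treatment starts. Report non-starters by arm.
5. **Families who decline randomisation** but consent to data use may be followed as non-randomised and kept out of the randomised comparison.

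The cost is mainly redrafting and one added criterion. More families may need to be approached, because unwilling ones are identified before the draw instead of after it.

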3.1. Trial objectives and definitions

The purpose of this study is to detect the differences, if any, between three well known, validated interceptive measures in case of maxillary permanent canine impaction, and to prospectively follow up on these treated patients until further permanent canine alignment in the dental arch is achieved. This long term follow up is necessary in order to evaluate the effects of the interceptive treatment on permanent maxillary canine eruption.

In the present study, a **maxillary permanent canine impaction** would be defined as the inability of this tooth to erupt, failure of eruption, deviation of the canine from its normal eruption pathway or retention of the canine in the maxilla.

Success of a particular interceptive measure would be defined as eruption of the canine without the need for surgical intervention and integrity of the adjacent teeth.

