3.2. Primary endpoints

The primary objective is to search for the most optimal interceptive action to prevent maxillary permanent canine impaction.

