- If the canine has not erupted yet, and positive progress was monitored at the 12 months follow up visit, a new LCAR will be taken to reevaluate canine eruption process, unless clear clinical indicators are present witnessing successful path of eruption, i.e. clear bulging of the canine crown in the vestibulum or clear canine cusp morphology visible in the buccal mucosa. Patient will then be instructed to report for follow up appointment at the time of canine eruption into the dental arch or at the latest after 6 months, being an extra 24 months recall. Anyhow, at the 18 months follow up visit, a reevaluation of the specific presenting malocclusion will be performed and the need for further orthopedic or fixed appliance treatment will be discussed with the patient or his/her parents/guardians. Normal orthodontic treatment can be performed if desired or needed at the time. In this case, further spontaneous canine eruption will be monitored during orthodontic treatment. Only at the end of this orthodontic treatment or, in case of no further treatment need, at the end of late mixed dentition transition into permanent dentition, a last follow up visit will be planned in order to evaluate the end result.

Follow up End result

As indicated above, two aspects of interceptive orthodontic treatment will be monitored. First of all the process of canine eruption being the maxillary permanent canine perforating the oral mucosa and erupting into the dental arch, and second the final position of the canine in the dental arch and its occlusion. Evaluation of the final result, eventually after orthodontic treatment, will include esthetics as well as functional occlusion and periodontal parameters giving an indication of gingival health. Assessment of the following parameters will be made: final position of the canine, final occlusion, root integrity of the canine and adjacent teeth, level of gingiva, general esthetic and functional result, gingival health. In order to do this, routine final records (clinical pictures, casts, LCAR or panoramic radiographs) will be taken as is performed for evaluation of standard orthodontic treatment.

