8.1. Sample size

Randomisation into expansion, extraction and control will be applied for patients without cross-bite having lack of space and – based on canine position and angulation - belonging to strata nCLB and nCLA. Within each of both strata, a randomisation will be performed using permuted blocks of varying size, yielding an equal number of patients in each of the three groups.

Success of the approach is defined as eruption without necessity of surgical intervention and integrity of the roots of the adjacent teeth. The primary endpoint is defined as the percentage success after 18 months. The trial is powered to show a difference between any of the pairs of groups. To have at least 80% power to show a higher success rate in one group compared to the other group, there are 78 subjects needed in each group assuming a success rate of 50% in the first group and 75% in the second group. The calculation is based on a two-sided χ^2 -test with alpha set at $0.05/3=0.0167$ to control the family-wise error rate at 5% (3 pairwise comparisons). However, to increase the amount of information for the development of a prediction model for success at 18 months (cfr. second aim of the study) it has been decided to increase the number of patients to 100 per group (300 patients in total).

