8.2. Analysis

The analysis of the primary endpoint will be based on a stratified χ^2 -test using a Bonferroni-Holm correction to correct for multiple testing (the strata are nCLB and nCLA). The same approach will be used for the comparison at the earlier timepoints (6 and 12 months). No interim analyses are planned, neither for efficacy, nor for futility. The analysis will be performed on an intent-to-treat basis.

A multivariable logistic regression model will be used to predict maxillary permanent canine impaction (=lack of success) on all included subjects. A backward selection procedure will be applied with 0.157 as critical level for the p-value. This critical value corresponds to the use of the Aikake Information Criterion (AIC) for model selection. With AIC we require that the increase in model χ^2 has to be larger than two times the degrees of freedom. This strategy provides a trade-off between erroneous inclusion and exclusion of covariates in a prediction model (Sauerbrei W. The use of resampling methods to simplify regression models in medical statistics. *Applied Statistics* 1999;48 (3):313–329.). The considered predictors are: strata formed by presence of cross-bite and parameters related to canine position and angulation, non-eruption, interceptive strategy, patient's age, stage of canine root formation, premature loss of deciduous teeth, familial history, space deficiency (arch length discrepancy).

As a sensitivity analysis, the prediction model will also be applied separately on the patients from the randomized and non-randomized part of the study.

9. Quality assurance

During this randomized clinical trial only standard operating procedures will be employed, such as i.e. removable expansion device, fixed expansion device, headgear, etc.. They are all validated, thoroughly described and widely used techniques. It will be up to the treating professional to decide for a given case which procedure to follow, in line with existing traditions in the specific collaborating centres. However, the main purpose should be attained which is expansion or in other words gaining extra space for tooth alignment. Depending on the interceptive treatment to be accomplished, decision will be taken to employ one specific treatment protocol to reach the goal set forward.

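### As planned, the analysis cannot separate delayed eruption from impaction: read literally, canines still progressing at 18 months share a class with surgical and arrested ones, and nothing later is analysed

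*Combined protocol and SAP*

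**What the plan says.** The aim is prevention. Section 3.2 states: "The primary objective is to search for the most optimal interceptive action to prevent maxillary permanent canine impaction". Section 8.1 defines the outcome: "Success of the approach is defined as eruption without necessity of surgical intervention and integrity of the roots of the adjacent teeth". It then sets the time: "The primary endpoint is defined as the percentage success after 18 months".

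Section 8.2 tests this endpoint with a stratified chi-squared test and a Bonferroni-Holm correction, and repeats the test only at 6 and 12 months. The prediction model, which section 8.1 describes as a model for success at 18 months, is to "predict maxillary permanent canine impaction (=lack of success) on all included subjects".

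Section 5.1, under the 18-month visit, deals with canines that have not erupted but showed progress at 12 months. A new apical radiograph is taken unless "clear clinical indicators are present witnessing successful path of eruption". The patient is then to return at eruption or "at the latest after 6 months, being an extra 24 months recall". Orthodontic treatment may begin at 18 months with the canine still unerupted. An end-result visit follows later.

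Section 8 mentions no analysis of 24-month status, end-result status, time to eruption or surgical exposure. The flowchart in section 3.6 has no 24-month column.

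**The concern.** Three kinds of canine can be unerupted or otherwise unsuccessful at 18 months: those exposed surgically or awaiting exposure, those that have stopped moving, and those still coming down. The success definition has no place for the third kind. On its literal terms they have not erupted, so they are not successes, and section 8.2 equates lack of success with impaction.

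Two results are affected. In the randomised comparison, a measure that only brings eruption forward could look as if it prevents impaction. In the prediction model, a canine that the protocol itself regards as on a good path would be coded as impacted, and the model would partly learn what makes a canine late. The extra comparisons at 6 and 12 months do not help, because they show timing before 18 months and not what happens to late canines afterwards.

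**Working it through.** **Inputs from section 8.1.** Success 50% vs 75%; two-sided alpha 0.05/3 = 0.0167; power 80%; 78 per group, raised to 100.

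**Assumed inputs.** The share of canines that erupt after 18 months is not in the documents, so it is varied below.

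**Formula.** Two-proportion test with pooled variance under the null and no continuity correction. Let d be the difference, m the mean of the two rates, A = 2.394 × √[2m(1 − m)] and B = √[p1(1 − p1) + p2(1 − p2)]. Then n = [(A + 0.8416 × B)/d]², and power = Φ[(d√n − A)/B].

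**Step 1: reproduce the plan's figure.** For 50% vs 75%, m = 0.625, A = 1.639 and B = 0.6614. So n = [(1.639 + 0.5567)/0.25]² = 77.1, rounded up to 78 as stated. Power is 80.5% at 78 per group. At 100 it is Φ[(2.5 − 1.639)/0.6614] = Φ(1.302) = 90.3%. The sample size arithmetic is sound.

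**Step 2: timing only.** Let both arms eventually reach 75% success. One arm has all its eventual erupters in by 18 months; the other has a fraction still to come. Prevention is then identical.

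| Late share of eventual erupters, slower arm | 18-month success, slower vs faster arm | Chance of a significant result, 100 per group |
|---|---|---|
| 1/3 | 0.75 × 2/3 = 50% vs 75% | 90.3% |
| 1/5 | 0.75 × 4/5 = 60% vs 75% | Φ[(1.5 − 1.586)/0.654] = 44.8% |
| 1/10 | 0.75 × 9/10 = 67.5% vs 75% | Φ[(0.75 − 1.532)/0.638] = 11.0% |

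In the first row, delay alone produces the whole difference that the trial is designed to find.

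**Step 3: equal late eruption.** Start from 50% vs 75% at 18 months and let the same share q of non-successes become successes later in both arms. Each rate becomes p + q(1 − p), and the difference becomes 0.25 × (1 − q).

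| q | Later success | Difference, points | Power at 100 per group |
|---|---|---|---|
| 0.1 | 55% vs 77.5% | 22.5 | 84.1% |
| 0.2 | 60% vs 80% | 20 | 76.1% |
| 0.3 | 65% vs 82.5% | 17.5 | 66.5% |
| 0.4 | 70% vs 85% | 15 | 55.9% |
| 0.5 | 75% vs 87.5% | 12.5 | 44.8% |

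Here a real prevention benefit survives, though a later test has less power to show it.

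**Limits.** The figures are for an unstratified pairwise test at the strictest Holm level, without dropout, for which the documents give no figure.

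**The case against.** A success endpoint at a fixed time is legitimate and is clearly stated here. That stands, and the 18-month endpoint should stay. Four stronger readings are tempting and should be resisted.

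- *The protocol declares progressing canines to be failures.* No sentence does. The words on a good eruption path come from a rule on when a radiograph can be skipped, not from an outcome definition. Failure is the literal consequence of the success definition, not a stated rule.
- *The trial cannot distinguish faster eruption from prevention.* Only the planned analysis cannot. Radiographic progress, surgical exposure, the 24-month recall and the end result are all to be recorded and could be analysed.
- *Section 3.1 admits that 18 months is too short.* It says "This long term follow up is necessary in order to evaluate the effects of the interceptive treatment on permanent maxillary canine eruption", but this refers to follow-up until the canine is aligned. It names no time and makes no judgement on 18 months.
- *A positive 18-month result would be largely wrong.* One can construct such a case. If 50% vs 75% became 75% vs 80% by 24 months, the test would be significant only about 6% of the time. That needs 25/50 = 50% late eruption in one arm against 5/25 = 20% in the other, and nothing in the documents supports such a gap. Moreover, section 5.1 allows canines unchanged between 6 and 12 months to go on to imaging and possibly surgery, so progressing canines are only part of the non-successes.

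The objection does not remove the gap itself. Section 5.1 foresees a group of canines for which section 8 has neither a category nor a later analysis. The 24-month visit in section 3.4 concerns the non-randomised group with adequate space and does not fill it.

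**Conclusion.** The point holds for the analysis as planned. On the literal reading, delayed and impacted canines are pooled in the primary comparison. In the prediction model the equation of impaction with lack of success labels both as impacted. No pre-specified analysis separates them.

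The size cannot be fixed from the documents. With no difference in prevention, the 18-month test could be significant anywhere from 11% to 90% of the time when one tenth to one third of eventual erupters in one arm are late. If late eruption is equally common among non-successes in both arms, the treatment benefit shrinks from 25 points to between 22.5 and 12.5 but does not vanish. All these shares are assumptions. This is a worthwhile, inexpensive improvement, not a flaw that invalidates the primary endpoint.

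**What to change.** Keep the 18-month primary endpoint and the sample size, and make these changes.

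1. In section 8.2, report 18-month non-success in two categories: (a) surgery done or indicated, no progress, or damage to adjacent roots; (b) unerupted but progressing.
2. In the prediction model, do not code category (b) as impacted without a sensitivity analysis that uses later status.
3. Pre-specify a supportive comparison of success by the 24-month recall, with the same stratified test and Holm correction. Use the full definition, including intact adjacent roots. Carry forward status already settled by 18 months (success or surgery), and state how canines neither settled nor progressing at that point are counted. The comparison should not be a condition for interpreting the primary result.
4. Add a sensitivity analysis that counts as non-success any canine whose orthodontic treatment began while it was unerupted.
5. In section 5.1, make clear that the 24-month outcome assessment covers every progressing, unerupted canine. The present wording could be read as limited to those with clear clinical signs. Add the visit to the flowchart.

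The cost is a little more analysis on a recall already foreseen. The supportive test will have less power: with a common late share of 20% it is already 76.1% at 100 per group, and 80% would need 109. Some eruptions between 18 and 24 months will also be affected by orthodontic treatment, which item 4 addresses only in part.
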